9.2.2. Exclusion Criteria

Patients meeting any of the following criteria will not be included in the study:

- 1. Have a diagnosis for the specific outcome under study within the 12 months prior to the index date (to distinguish the recording of previous events from true new events) and at any time prior to the index date for diabetes type 1
- 2. Have received any RSV vaccinations during the 12-month baseline period

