9.3.2. Outcome Definitions

9.3.2.1. Safety Outcomes

Outcomes will be defined consistently across the data sources to the fullest extent possible.

Body system/ classification	Adverse event of special interest	Estimated risk window (days) ^a .	Analytic Approach
Autoimmune diseases	Acute disseminated encephalomyelitis	1-42 ^{39, b} .	Cohort/SCRI
	Diabetes mellitus type I	1-365	Cohort
	Guillain-Barré syndrome	1-42 ^{39, b} .	Cohort/SCRI
	Narcolepsy	1-365°.	Cohort
	Thrombocytopenia (idiopathic)	$1-42^{40}$	Cohort/SCRI
	Thrombosis thrombocytopenia syndrome	1-15 ³⁹	Cohort/SCRI
Cardiovascular system ^{d.}	Acute cardiovascular injury	$1-28^{41}$	Cohort
-	Arrhythmia Specific subgroups of patients with atrial fibrillation and supraventricular arrhythmias will be identified for additional analyses	1–365 ^{e. g.}	Cohort
	Coronary artery disease	1–365	Cohort

Table 1List of Select Adverse Events of Special Interest

PFIZER CONFIDENTIAL

CT24-WI-GL02-RF02 5.0 Non-Interventional Study Protocol Template For Secondary Data Collection Study 01-Aug-2023 Page 30 of 72

Body system/	Adverse event of special interest	Estimated risk	Analytic Approach	
classification		window (days) ^a .		
	Heart failure	1–365	Cohort	
	Microangiopathy	1–365	Cohort	
	Myocarditis	1-21	Cohort/SCRI	
	Myocarditis and pericarditis	1-7	Cohort/SCRI	
	Pericarditis	1-14	Cohort/SCRI	
	Stress cardiomyopathy	1-365	Cohort	
Cinculatory		1-303 $1-28^{39, f.}$	Cohort/SCRI	
Circulatory	Coagulation disorders: Disseminated intravascular	1-20	Conort/SCRI	
system				
	coagulation, venous			
	thromboembolism (pulmonary			
	embolism, deep vein thrombosis),			
	thrombotic microangiopathy,			
	cerebral venous thrombosis,			
	thrombotic thrombocytopenia			
	syndrome, ischemic stroke,			
	myocardial infarction, haemorrhage	-		
	Single organ cutaneous vasculitis	1-28 ^{f.}	Cohort/SCRI	
	Thrombocytopenia with venous	1–15	Cohort/SCRI	
	thromboembolism			
Nerves and	Bell's palsy	1-42 ³⁹	Cohort/SCRI	
central nervous	Generalised convulsion	0-42 ^{39, , g.}	Cohort/SCRI	
system	Meningoencephalitis	1-42 ³⁹	Cohort/SCRI	
	Transverse myelitis	1–42 ^{39, b. c.}	Cohort/SCRI	
Respiratory	Acute respiratory distress syndrome	1–365	Cohort	
system				
Skin and mucous	•	1–42	Cohort	
membrane, bone				
and joints system				
Other system	Anaphylaxis	0-1 ^{39, , g.}	Cohort/SCRI	
	Death (any causes)	0–365 ^{, g.}	Cohort	

Table 1 List of Select Adverse Events of Special Interest

Notes:

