9.3.2.2. Outcome Identification

Outcomes will be identified in participant data sources with algorithms based on codes for diagnoses, procedures, and treatments. Proposed algorithms and diagnostic codes for all prespecified outcomes will incorporate definitions developed by the ACCESS project⁴² and will be described in more detail in the statistical analysis plan (SAP). ACCESS developed harmonised definitions and code lists for the outcomes listed in **Table 1**. for application to routine healthcare data sources across Europe. These definitions were subsequently used for the calculation of background outcome rates to contextualize emerging COVID-19 vaccine safety data. Healthcare data covering approximately 130 million lives across 7 European countries and 22 data sources were used to generate background rates. Algorithms will be tailored to the data source and will consider the provenance of the medical records that have identified the outcome, e.g., primary care, access to hospital care, and access to emergency care.⁴³ Multiple algorithms for the same outcome may be included in the analysis, to assess the potential impact of differential misclassification. Several outcomes have been validated in previous VAC4EU studies.

Outcome onset will be primarily defined as the date of the healthcare encounter associated with the relevant diagnostic code. Most outcomes of interest are serious enough to warrant healthcare consultation close to the time of symptom onset. However, for those outcomes that might include a lag between the onset of symptoms and diagnosis in a healthcare setting (e.g., DVT or diabetes type 1), algorithms may incorporate additional considerations to capture onset dates closer to the time of symptom onset. These considerations will be detailed in the SAP. Sensitivity analyses may also be incorporated to assess assumptions around outcome onset for relevant outcomes.

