9.3.3. Covariate Definitions

The following variables will be assessed at the date of vaccine administration (i.e, index date for the vaccinated cohort in the comparative cohort design and SCRI design) or matched index date (for the unvaccinated cohort in the comparative cohort design) or during the 12month baseline period. These variables will be used to further characterise the patient populations of interest and/or to control for confounding. The prespecified outcomes may

PFIZER CONFIDENTIAL CT24-WI-GL02-RF02 5.0 Non-Interventional Study Protocol Template For Secondary Data Collection Study 01-Aug-2023 Page 32 of 72 have different sets of risk factors, and outcome-specific analyses may contain different covariate sets. Covariates with sufficient availability across data sources include:

- Demographics
 - Age which may be categorised as age categories in line with published background incidence rates from ACCESS (60-64, 65-69, 70-79, 80+ years) dependent on sample size.
 - o Sex
 - Race and/or ethnicity, as appropriate in each country
 - Geographic region, as appropriate in each country
- Date of vaccination (categorised by month or year to assess trends in vaccine uptake)
- Comorbidities
 - History of anaphylaxis
 - History of allergies
 - Diabetes mellitus (types 1 and 2)
 - Hypertension
 - Cardiovascular disease
 - Cerebrovascular disease
 - Chronic respiratory disease (asthma, COPD, chronic bronchiectasis)
 - Haematological conditions
 - o CKD
 - Dementia (i.e, Alzheimer's disease and related disorders, senile dementia)
 - Chronic liver disease
 - o Cancer
 - Autoimmune disorders
 - Influenza infection or other respiratory infections
 - Charlson Comorbidity Index (may be included as the composite scale, or the scale components may be included as individual terms)
- Comedication use (prescriptions or dispensing, no over-the-counter medication use)
 - Analgesics
 - Antibiotics
 - Antiviral medications
 - Corticosteroids

PFIZER CONFIDENTIAL

CT24-WI-GL02-RF02 5.0 Non-Interventional Study Protocol Template For Secondary Data Collection Study 01-Aug-2023 Page 33 of 72

- o Non-steroidal anti-inflammatory drugs
- Psychotropics
- o Statins
- o Novel oral anticoagulants
- o Warfarin
- Number of medications used
- Healthcare utilisation
 - Number of hospitalisations
 - Number of emergency department visits
 - o Skilled nursing facility, nursing home, or extended care facility stay
 - Primary care utilisation
 - Cancer screening

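### The type 1 diabetes analysis excludes only people with a prior type 1 diagnosis, so people with other known diabetes stay at risk and a relabelling may count as a new event unless the outcome algorithm prevents it

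*Protocol*

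**What the plan says.** Section 9.2.2 of the protocol, exclusion 1, applies to people who "Have a diagnosis for the specific outcome under study within the 12 months prior to the index date". Its stated purpose is "to distinguish the recording of previous events from true new events". One outcome gets a longer look-back: the exclusion runs "at any time prior to the index date for diabetes type 1".

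Table 1 in Section 9.3.2.1 lists "Diabetes mellitus type I" among the autoimmune diseases, with a risk window of days 1 to 365 and the cohort design only.

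On ascertainment, Section 9.3.2.2 states: "Outcomes will be identified in participant data sources with algorithms based on codes for diagnoses, procedures, and treatments". Algorithm detail is deferred to the SAP. The only remark there that is specific to type 1 diabetes concerns delay between symptoms and diagnosis, for which "algorithms may incorporate additional considerations to capture onset dates closer to the time of symptom onset". It does not touch on earlier diabetes of another type.

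Section 9.3.3 lists both types of diabetes as baseline comorbidities. Its comedication list does not name glucose-lowering drugs. Covariates are assessed at index or in the preceding 12 months.

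**The concern.** The longer look-back shows that the authors saw pre-existing diabetes as a problem for this outcome, but the rule deals with it only when the earlier record already says type 1. Someone with known type 2 or unspecified diabetes, or on glucose-lowering treatment, passes the exclusion and enters the type 1 risk set. If a type 1 code appears for that person within the 365-day window, it may be a change of label on old disease.

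Two features raise the stakes. Eligibility selects adults aged 60 and over with renal or hepatic impairment or immunosuppression, including long-term corticosteroid use, so people with prior diabetes will be present. The protocol does not say how many. Second, type 1 diabetes has no self-controlled analysis behind it, so the cohort IRR stands alone. False events in that IRR could hide a real effect or, if re-coding differs between cohorts, create an apparent one.

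**Working it through.** **The plan's own figures.** The protocol gives no rate, sample size or power for type 1 diabetes. The nearest figure with the same design and a 365-day window is arrhythmia in Table 2 (Section 9.5): background risk 0.02, IRR 2, two-sided alpha 0.05, power 80%, equal cohorts. With an unpooled rate-difference formula,

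n = (z₀.₉₇₅ + z₀.₈₀)² × λ₀(1 + IRR) / [λ₀(IRR − 1)]² = 7.849 × 0.06 / 0.0004 = 1,177.3, rounded up to 1,178.

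This matches Table 2, so the same formula is used below for the effect on sample size.

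**Dilution if re-coding is equal in both cohorts.** Let t be the true type 1 onset rate in the unvaccinated and m the rate of re-codings counted as events, both per 100,000 person-years over the whole cohort. Then

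observed IRR = (IRR × t + m) / (t + m).

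The absolute rate difference t(IRR − 1) is unchanged and only the variance term grows, so the required n is multiplied by

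[t(1 + IRR) + 2m] / [t(1 + IRR)].

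Inputs, all assumed: true IRR 3, t = 5 or 10, m from 2.5 to 60.

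| m | Observed IRR, t = 5 | Observed IRR, t = 10 | n multiplier, t = 5 | n multiplier, t = 10 |
|---|---|---|---|---|
| 2.5 | 17.5/7.5 = 2.33 | 32.5/12.5 = 2.60 | 25/20 = 1.25 | 45/40 = 1.13 |
| 10 | 25/15 = 1.67 | 40/20 = 2.00 | 40/20 = 2.0 | 60/40 = 1.5 |
| 30 | 45/35 = 1.29 | 60/40 = 1.50 | 80/20 = 4.0 | 100/40 = 2.5 |
| 60 | 75/65 = 1.15 | 90/70 = 1.29 | 140/20 = 7.0 | 160/40 = 4.0 |

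To put m in context, suppose 25% of the cohort has other known diabetes (also assumed). Then m = 25,000 × the yearly re-coding rate in that group, so m = 2.5, 10 and 60 correspond to 0.01%, 0.04% and 0.24% a year.

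**If re-coding differs between cohorts.** Let d be the ratio of the re-coding rate in the vaccinated to that in the unvaccinated. Then observed IRR = (IRR × t + d × m) / (t + m). Take t = m, so that half of unvaccinated events are false:

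- True IRR 1: d = 0.8 gives 0.90, d = 1.2 gives 1.10, d = 1.5 gives 1.25.
- True IRR 2: d = 1 gives 1.50, d = 2.5 gives 2.25.

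The direction is therefore not fixed.

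**Whether other parts of the plan remove the problem.** The weighting and doubly robust adjustment in Section 9.7.3.1 can balance the share of people with prior diabetes, but they leave the false events in both numerators. The narrow and broad algorithms in Section 9.7.4 are conditional on feasibility and vary the outcome definition, not eligibility. The example negative controls there (accidental poisoning, appendicitis, cataracts, non-vertebral fractures) would not reveal re-coding of diabetes.

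**The case against.** The strongest reply is that the protocol nowhere says a re-coding counts as an event. Section 9.3.2.2 allows algorithms that combine diagnoses, procedures and treatments and leaves their detail to the SAP; a type 1 algorithm could require no earlier diabetes code or a particular treatment pattern. That stands, and it makes the consequence conditional. It does not remove the point, because the eligibility rule is fixed in Section 9.2.2 itself and is narrower than its stated aim.

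The covariate list is also weak evidence about who is at risk. It names type 1 as well as type 2, serves every outcome, and Section 9.3.3 allows covariate sets to differ by outcome. The point rests on the wording of exclusion 1 and the absence of any other rule.

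A reader might infer that the bias must be towards 1. That needs equal re-coding. Section 9.9 does not anticipate differential reporting, but it also names differential ascertainment as a potential limitation and does not secure equality. A reader might further infer that re-codings outnumber true onsets. No figure in the protocol supports that, and at 2.5 per 100,000 the dilution is modest.

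Finally, excluding all prior diabetes loses true late-onset cases first labelled type 2. That is a real trade of sensitivity for specificity, which is why the present rule should be retained as a sensitivity analysis.

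**Conclusion.** The point holds as a shortcoming of a stated rule. Exclusion 1 does not keep previously known diabetes of another type out of the type 1 analysis, so it falls short of its purpose of separating old records from new events. False events follow only if the SAP algorithm does not itself require absence of earlier diabetes. The size cannot be derived from the protocol. On the assumed rates shown, a true IRR of 3 could be seen as anything from 2.60 to 1.15 under equal re-coding, and unequal re-coding can bias the result in either direction. The protocol does not support the stronger claims that relabelled cases will be counted or that a real effect would be masked. This is a low-cost improvement to one outcome and does not threaten the study as a whole.

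**What to change.** In Section 9.2.2, for the type 1 diabetes outcome only, exclude anyone with any diabetes diagnosis (type 1, type 2, unspecified or secondary) or any glucose-lowering drug record at any available time before index. Keep the type-1-only exclusion as a sensitivity analysis, so that the two results show how much relabelling matters. The drug criterion is useful because diagnoses are not captured equally in all sources: in SNDS, for example, outpatient claims carry no indication or results (Section 9.4.5).

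The cost is one added line in the protocol and some added extraction. Glucose-lowering drugs are not in the comedication list of Section 9.3.3, and the look-back must reach beyond the 12-month covariate window, although all five sources hold prescription or dispensing records. The at-risk group becomes smaller, and people first labelled type 2 and later reclassified are no longer studied in the main analysis.

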9.2.3. Source Population

The source population for the cohort design will be composed of all individuals registered in each of the participating healthcare data sources. The selected European populations are those underlying the data sources listed in Section 9.2.

9.2.4. Study Period

The study period will start from 23 August 2022 to allow at least 12 months of administrative enrolment before vaccination with vaccination possible from the date of approval in the EU. Data collection will extend through a minimum of three vaccination seasons (2023, 2024, and 2025). Patient follow-up will last for up to 12 months post-vaccination depending on the outcome; therefore, data collection will extend through the end of 2026, at a minimum. Vaccine uptake will be periodically monitored to inform the overall length of the study period, and additional vaccination seasons (with 12-month post-vaccination follow-up) may be added based on vaccine uptake and exposure accrual. Time lags for data availability will be taken into account for analysis and reporting purposes.

9.3. Variables

9.3.1. Exposure Definition

Exposure will be based on recorded prescription, dispensing, or administration of ABRYSVO. Vaccine receipt and date of vaccination will be obtained from all available sources that capture ABRYSVO vaccination, such as pharmacy dispensing records, general practice records, immunization registers, vaccination records, medical records, or other secondary data sources. Depending on the data source, vaccines will be identified via

PFIZER CONFIDENTIAL CT24-WI-GL02-RF02 5.0 Non-Interventional Study Protocol Template For Secondary Data Collection Study 01-Aug-2023

Page 28 of 72

nationally used product codes where possible. The main exposure of interest is in the receipt of ABRYSVO.

- **CPRD Aurum (UK):** Data on vaccine exposure will be identified using CPRD Product Codes (PRODCODE ID's) and/or Medical Codes (MEDCODE ID's) based on available codes in CPRD product and medical dictionaries. Vaccination data originate from the patient primary care electronic medical records held within CPRD. The information captured at the individual patient level includes the name of the vaccine; manufacturing company; dose; stage of the vaccine schedule (if applicable); administration route; administration location (e.g., general practice); date of administration; and medical observations, events, referrals, test results, and prescribed medications recorded by the GP prior to, on, or after the vaccination date.
- VID (ES): Data on vaccine exposure are obtained from patient level electronic records within the vaccine information system which captures information on vaccine type, manufacturer, number of doses, location and administration date, adverse reactions related to vaccines, and if applicable, risk groups. Vaccines information in the VID is updated daily.
- **SIDIAP (ES):** Data are available on all routine childhood and adult immunizations, including the antigen and the number of administered doses. Vaccination information originates from patient electronic medical records. For each patient, SIDIAP has the date and centre of administration, dose, brand, reasons for vaccination (e.g., risk of group), and other information related to vaccination.
- **EpiChron (ES):** The EpiChron cohort provides data of individuals' pharmacotherapeutic history, including vaccination, with prescriptions and dispensation of drugs in community pharmacies, coded according to the WHO ATC classification system.
- **SNDS (FR):** Exposure information is captured based on vaccines dispensed in community outpatient pharmacies. Exposure information will be coded using the ATC classification system as well as a specific French pharmacy codes (CIP) and European Pharmaceutical Market Research Association codes, with dates of prescription and dispensing.

9.3.1.1. Comparative Cohort Design

The exposure cohorts for the comparative cohort design will be defined as follows:

• The vaccinated cohort will be defined as individuals who were administered ABRYSVO.

To be included in the unvaccinated cohort, individuals must meet the following criteria:

• No vaccine record on index date: They must not have a record of receiving any vaccine, including the RSV vaccines, on the index date.

PFIZER CONFIDENTIAL

CT24-WI-GL02-RF02 5.0 Non-Interventional Study Protocol Template For Secondary Data Collection Study 01-Aug-2023 Page 29 of 72 • **No RSV vaccination in baseline period**: They must not have a record of receiving any RSV vaccine during the 12-month baseline before the index date.

Note: If individuals in the unvaccinated cohort receive ABRYSVO during the follow-up period, they will be censored in the unvaccinated cohort and become eligible for inclusion in the vaccinated cohort if all other eligibility criteria are met.

9.3.1.2. SCRI Design

For the SCRI design, person-time in the risk interval will be considered "exposed," while person-time in the control interval will be considered "unexposed." Risk intervals will be specific to the outcome of interest and are defined to reflect the

duration of time post-vaccine exposure that an incident post-vaccine event is expected to occur based on biological plausibility. Events known to have a risk window limited to a defined period after vaccination are not well known for ABRYSVO and other RSV vaccines, therefore event-specific intervals will be defined based on prior post-marketing studies of other vaccines (where applicable), clinical trial data (where applicable), and passive post-marketing surveillance activities (as they become available).

9.3.2. Outcome Definitions

9.3.2.1. Safety Outcomes

Outcomes will be defined consistently across the data sources to the fullest extent possible.

Body system/ classification	Adverse event of special interest	Estimated risk window (days) ^a .	Analytic Approach
Autoimmune diseases	Acute disseminated encephalomyelitis	1-42 ^{39, b} .	Cohort/SCRI
	Diabetes mellitus type I	1-365	Cohort
	Guillain-Barré syndrome	1-42 ^{39, b} .	Cohort/SCRI
	Narcolepsy	1-365°.	Cohort
	Thrombocytopenia (idiopathic)	$1-42^{40}$	Cohort/SCRI
	Thrombosis thrombocytopenia syndrome	1-15 ³⁹	Cohort/SCRI
Cardiovascular system ^{d.}	Acute cardiovascular injury	$1-28^{41}$	Cohort
-	Arrhythmia Specific subgroups of patients with atrial fibrillation and supraventricular arrhythmias will be identified for additional analyses	1–365 ^{e. g.}	Cohort
	Coronary artery disease	1–365	Cohort

Table 1List of Select Adverse Events of Special Interest

PFIZER CONFIDENTIAL

CT24-WI-GL02-RF02 5.0 Non-Interventional Study Protocol Template For Secondary Data Collection Study 01-Aug-2023 Page 30 of 72

Body system/	Adverse event of special interest	Estimated risk	Analytic Approach	
classification		window (days) ^a .		
	Heart failure	1–365	Cohort	
	Microangiopathy	1–365	Cohort	
	Myocarditis	1-21	Cohort/SCRI	
	Myocarditis and pericarditis	1-7	Cohort/SCRI	
	Pericarditis	1-14	Cohort/SCRI	
	Stress cardiomyopathy	1-365	Cohort	
Cinculatory		1-303 $1-28^{39, f.}$	Cohort/SCRI	
Circulatory	Coagulation disorders: Disseminated intravascular	1-20	Conort/SCRI	
system				
	coagulation, venous			
	thromboembolism (pulmonary			
	embolism, deep vein thrombosis),			
	thrombotic microangiopathy,			
	cerebral venous thrombosis,			
	thrombotic thrombocytopenia			
	syndrome, ischemic stroke,			
	myocardial infarction, haemorrhage	-		
	Single organ cutaneous vasculitis	1-28 ^{f.}	Cohort/SCRI	
	Thrombocytopenia with venous	1–15	Cohort/SCRI	
	thromboembolism			
Nerves and	Bell's palsy	1-42 ³⁹	Cohort/SCRI	
central nervous	Generalised convulsion	0-42 ^{39, , g.}	Cohort/SCRI	
system	Meningoencephalitis	1-42 ³⁹	Cohort/SCRI	
	Transverse myelitis	1–42 ^{39, b. c.}	Cohort/SCRI	
Respiratory	Acute respiratory distress syndrome	1–365	Cohort	
system				
Skin and mucous	•	1–42	Cohort	
membrane, bone				
and joints system				
Other system	Anaphylaxis	0-1 ^{39, , g.}	Cohort/SCRI	
	Death (any causes)	0–365 ^{, g.}	Cohort	

Table 1 List of Select Adverse Events of Special Interest

Notes:

a. Day 0 is the date of vaccine administration (i.e, index date for the vaccinated cohort in the comparative cohort design and SCRI design) or matched index date (for the unvaccinated cohort in the comparative cohort design) b. To align with ongoing postmarketing study C3671031, A Post-Authorization Safety Study of Guillain-Barré Syndrome (GBS) Following ABRYSVOTM Among Older Adults in the United States, sensitivity analyses will be performed for GBS, acute disseminated encephalomyelitis, and transverse myelitis using shorter risk intervals of 1-21 days, 5-28 days, and 1-21 days, respectively. Further details are outlined in Section 9.7.4. c. Published risk and control intervals for demyelinating diseases and cranial disorders were applied to transverse myelitis and narcolepsy/cataplexy.

d. Please note that alternative risk windows were reported in other studies.

e. To align with ongoing postmarketing study C3671037, A Post-Authorization Safety Study of Atrial Fibrillation Following Respiratory Syncytial Virus Vaccine (ABRYSVOTM) Among Older Adults in the

PFIZER CONFIDENTIAL

CT24-WI-GL02-RF02 5.0 Non-Interventional Study Protocol Template For Secondary Data Collection Study 01-Aug-2023

Page 31 of 72

Table 1	List of Select Adverse Events of Special Interest
---------	---

Body system/	Adverse event of special interest	Estimated risk	Analytic Approach
classification		window (days) ^a .	

Veterans Affairs Health System, sensitivity analysis will be performed for atrial fibrillation and supraventricular arrhythmias using a shorter risk interval of 0-3 days. Alternative risk intervals of 0-1 day or 0-30 days may also be considered. Details are provided in Section 9.7.4.

f. Similar risk and control intervals were applied to all cardiovascular and haematological disorders characterised by damage to the blood vessels and/or arteries and clotting (i.e, coagulation disorders and single organ cutaneous vasculitis).

g. Risk intervals for most outcomes start on Day 1 post-index, but for some outcomes, the risk interval starts on the day of vaccination due to biological plausibility of rapid onset following vaccination.

